10.1.3 Additional Points to Consider for PTEs and AEs

An untoward finding generally may:

- Indicate a new diagnosis or unexpected worsening of a pre-existing condition. (Intermittent events for pre-existing conditions underlying disease should not be considered PTEs or AEs.)
- Necessitate therapeutic intervention.
- Require an invasive diagnostic procedure.
- Require discontinuation or a change in dose of study medication or a concomitant medication.
- Be considered unfavorable by the investigator for any reason.
- PTEs/AEs caused by a study procedure (e.g., a bruise after blood draw) should be recorded as a PTE/AE.

Diagnoses vs. signs and symptoms:

- Each event should be recorded to represent a single diagnosis. Accompanying signs (including abnormal laboratory values or ECG findings) or symptoms should NOT be recorded as additional AEs. If a diagnosis is unknown, sign(s) or symptom(s) should be recorded appropriately as a PTE(s) or as an AE(s).

Laboratory values and ECG findings:

- Changes in laboratory values or ECG parameters are only considered to be PTEs or AEs if they are judged to be clinically significant (i.e., if some action or intervention is required or if the investigator judges the change to be beyond the range of normal physiologic fluctuation).

A laboratory re-test and/or continued monitoring of an abnormal value are not considered an intervention. In addition, repeated or additional noninvasive testing for verification, evaluation, or monitoring of an abnormality is not considered an intervention.

- If abnormal laboratory values or ECG findings are the result of pathology for which there is an overall diagnosis (e.g., increased creatinine in renal failure), the diagnosis only should be reported appropriately as a PTE or as an AE.

Pre-existing conditions:

- Of pre-existing conditions (present at the time of signing of informed consent), events that are considered accompanying symptoms of MDD should NOT be recorded as concurrent medical conditions, PTEs, or AEs.

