10.2.1.2 PTE and AE Reporting

At each study visit, the investigator will assess whether any subjective AEs have occurred. A neutral question, such as "How have you been feeling since your last visit?" may be asked. Subjects may report AEs occurring at any other time during the study.

Subjects experiencing a serious PTE must be monitored until the symptoms subside and any clinically relevant changes in laboratory values have returned to baseline or until there is a satisfactory explanation for the change (for permanent or irreversible PTEs). Non-serious PTEs, related or unrelated to the study procedure, need not to be followed-up for the purposes of the protocol.

All subjects experiencing AEs, whether considered associated with the use of the study medication or not, must be monitored until the symptoms subside and any clinically relevant changes in laboratory values have returned to baseline or until there is a satisfactory explanation for the change (for permanent or irreversible AEs). All PTEs and AEs will be documented in the PTE/AE page of the eCRF, whether or not the investigator concludes that the event is related to the drug treatment. The following information will be documented for each event:

1. Event term
2. Start and stop date
3. Frequency
4. Severity
5. Investigator's opinion of the causal relationship between the event and administration of study medication(s) (probable, possible, not related) (not completed for PTEs).
6. Investigator's opinion of the causal relationship to study procedure(s), including the details of the suspected procedure.
7. Action concerning study medication (not applicable for PTEs)
8. Outcome of event
9. Seriousness
10. Classification as special interest AEs (Yes or No)

C-SSRS will not be used as a primary means to collect AEs. However, should the investigator become aware of a potential AE through the information collected with this instrument, proper follow-up with the patient for medical evaluation should be undertaken. If it is determined that an AE not previously reported has been identified through this follow-up, normal reporting requirements should be applied.

AEs and serious PTEs will be followed up until resolution or until the investigator judges that further follow-up is not necessary.

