13.1.5 Safety Analysis

AEs

The definition of treatment-emergent adverse events (TEAE) will be described in the statistical analysis plan (SAP). TEAEs will be summarized using the safety analysis set. TEAEs will be coded using the MedDRA and will be summarized by system organ class (SOC) and preferred term (PT). No statistical testing or inferential statistics will be generated.

A subject who has developed a same TEAE more than once will be counted as 1 subject in the severity category corresponding to the maximum severity of the event.

Clinical Laboratory Test, Weight, Vital Signs, and ECG

Summary statistics of observed values and changes at each time point (values at each time point in the double-blind treatment period – baseline) will be calculated for clinical laboratory tests, vital signs, ECG parameters, and weight for each treatment group. Incidences of values that are outside normal ranges and are potentially and clinically significant will be calculated.

C-SSRS

Descriptive statistics of C-SSRS will be calculated at each time point for each treatment group.

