3.3 Laboratory and Other Safety Data

3.3.1 Laboratory Test Results

3.3.1.1 Hematology and Serum Chemistry

Analysis Set: Safety Analysis Set

Analysis Hematology

Variable(s): RBC WBC Hemoglobin

WBC Differentials (Neutrophils, Eosinophils, Basophils, Lymphocytes, Monocytes)

Serum Chemistry

(Conjugated

Bilirubin)

Blood Urea Nitrogen Uric Acid Glucose

Calcium Chloride Triglycerides

Total Cholesterol HDL Cholesterol LDL Cholesterol

(Direct Method)

Categories: Results of judgement [Low, Normal, or High relative to the normal reference range]

based on the

reference range

Results based [Meet PCS Criteria, Does not meet PCS Criteria]
on PCS Criteria

Visit: Screening, Placebo Lead-in, Baseline, Week 4, and Week 8

PCS: Baseline (entire pre-dose period), Entire post-dose period

Analytical The following summaries will be provided for the above analysis variable(s)

Method(s):

- (1) Descriptive statistics for observed values at each visit and changes from baseline at each visit (each post-dose visit [Week 4, Week 8] - Baseline)
- (2) Plots over time for each subject
- (3) Shift tables at baseline and each post-dose visit of the results of judgement based on the reference range.
- (4) Frequency distributions of the results based on PCS Criteria during the entire post-dose period

Refer to the Appendix of this Statistical Analysis Plan if a laboratory parameter has lower or upper PCS Criteria.

(5) Shift tables of the results based on PCS Criteria at baseline (entire pre-dose period) and during the entire post-dose period

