Most Recent Attempt (Screening Only)	[No physical damage or extremely mild physical damage, Mild physical damage, Moderate physical damage that requires treatment, Slightly severe physical damage that is highly likely to require hospitalization and intensive treatment, Severe physical damage that requires hospitalization and intensive treatment, Death]
Details of no physical damage	[Suicidal behavior that is less likely to bear physical damage, Suicidal behavior that is highly likely to bear physical damage but less likely to die, Suicidal behavior that is highly likely to die even with treatment]
Most Highly Lethal Actual Attempt	[No physical damage or extremely mild physical damage, Mild physical damage, Moderate physical damage that requires treatment, Slightly severe physical damage that is highly likely to require hospitalization and intensive treatment, Severe physical damage that requires hospitalization and intensive treatment, Death]
Details of no physical damage	[Suicidal behavior that is less likely to bear physical damage, Suicidal behavior that is highly likely to bear physical damage but less likely to die, Suicidal behavior that is highly likely to die even with treatment]

First Attempt (Screening Only)	[No physical damage or extremely mild physical damage, Mild physical damage, Moderate physical damage that requires treatment, Slightly severe physical damage that is highly likely to require hospitalization and intensive treatment, Severe physical damage that requires hospitalization and intensive treatment, Death]
Details of no physical damage	[Suicidal behavior that is less likely to bear physical damage, Suicidal behavior that is highly likely to bear physical damage but less likely to die, Suicidal behavior that is highly likely to die even with treatment]
Visit:	Screening, Placebo Lead-in, Baseline, Week 1, Week 2, Week 4, Week 6, and Week 8
Analytical Method(s):	For each variable, summaries (1) will be provided by treatment group. (1) Frequency distributions at each visit

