3.3.2.4 Summary of Columbia-Suicide Severity Rating Scale (C-SSRS)

Analysis Set:	Safety Analysis Set
Analysis Variable(s):	Absence of Suicidal Ideation and Suicidal Behavior [Yes, No]
	Non-Suicidal Self-Injurious Behavior [Yes, No]
	Presence of Suicidal Ideation or Suicidal Behavior [Yes, No]
	Suicidal Ideation [Yes, No]
	Wish to be Dead [Yes, No]
	Non-Specific Active Suicidal Thoughts [Yes, No]
	Active Suicidal Ideation with Any Methods (Not Plan) without Intent to Act [Yes, No]
	Active Suicidal Ideation with Some Intent to Act, without Specific Plan [Yes, No]

Active Suicidal Ideation with Specific Plan and Intent	[Yes, No]
Suicidal Behavior	[Yes, No]
Preparatory Acts or Behavior	[Yes, No]
Aborted Attempt	[Yes, No]
Interrupted Attempt	[Yes, No]
Actual Attempt	[Yes, No]
Completed Suicide	[Yes, No]
Visit:	Screening, Baseline (Entire Pre-dose Period), Entire Post-dose Period
Analytical	For each variable, summaries (1) will be provided by treatment group.
Method(s):	(1) Frequency distributions at each visit

4 Significance Level and Confidence Coefficient

- Significance level: 5% (two-sided test)
- Confidence coefficient: 95% (two-sided)

* No statistical testing will be performed if there are less than 5 subjects.

Amendment History (Version Management)

Version	Date	Author	Comments
1	9 June, 2015	PPD	Preparation of Version 1
2	23 May, 2018		Preparation of Version 2

[Appendix 1] Change Comparison Table for Lu AA21004/CCT-004

Page	Before Change	After Change	Reason for Change
Cover	No caption Version 1: Prepared on 9 June, 2015	No caption Version 2: Prepared on 24 May, 2018	
4	Definition of TIME WINDOW -15	Definition of TIME WINDOW -12	Due to error in writing
4	Definition of TIME WINDOW -14 - -5	Definition of TIME WINDOW -11 - -5	Due to error in writing
5	Definition of TIME WINDOW -15	Definition of TIME WINDOW -12	Due to error in writing
5	Definition of TIME WINDOW -14 - -5	Definition of TIME WINDOW -11 - -5	Due to error in writing
6	Definition of TIME WINDOW -15	Definition of TIME WINDOW -12	Due to error in writing
6	Definition of TIME WINDOW -14 - -5	Definition of TIME WINDOW -11 - -5	Due to error in writing
7	Definition of TIME WINDOW -15	Definition of TIME WINDOW -12	Due to error in writing
7	Definition of TIME WINDOW -14 - -5	Definition of TIME WINDOW -11 - -5	Due to error in writing

Page	Before Change	After Change	Reason for Change

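### The C-SSRS tables give separate pre-dose and post-dose frequencies, so they cannot count subjects whose suicidal ideation or behaviour is new or worse after dosing

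*SAP*

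**What the plan says.** The C-SSRS is a safety endpoint (Protocol 5.2.3) and is given at Visits 1 to 8 (Protocol Appendix A). For its analysis, Protocol 13.1.5 says: "Descriptive statistics of C-SSRS will be calculated at each time point for each treatment group".

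The SAP has two C-SSRS tables, both by treatment group:

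- SAP 3.3.2.3 lists every item at "Screening, Placebo Lead-in, Baseline, Week 1, Week 2, Week 4, Week 6, and Week 8", as frequencies.
- SAP 3.3.2.4 lists each ideation and behaviour category as yes or no at "Screening, Baseline (Entire Pre-dose Period), Entire Post-dose Period". The only method is "1) Frequency distributions at each visit".

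For other safety data the SAP does compare within subject. SAP 3.3.1.1 plans "Shift tables at baseline and each post-dose visit of the results of judgement based on the reference range" and also "Shift tables of the results based on PCS Criteria at baseline (entire pre-dose period) and during the entire post-dose period". Shift tables are also planned for urinalysis (3.3.1.2) and ECG interpretation (3.3.2.2).

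On adverse events, Protocol 10.2.1.2 says "C-SSRS will not be used as a primary means to collect AEs". For conditions already present at consent, Protocol 10.1.3 says "events that are considered accompanying symptoms of MDD should NOT be recorded as concurrent medical conditions, PTEs, or AEs".

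**The concern.** Suicidality is the safety question that this trial inherits. Protocol 4.1.3 reports suicidal ideation as an adverse event in the earlier Japanese study (CCT-003) in 8 subjects (6.6%) on 10 mg, 2 (1.6%) on placebo and 1 (0.8%) on 5 mg. The present trial studies 10 mg again and adds 20 mg.

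The natural question for a scale given at every visit is how many subjects had no ideation before dosing and some afterwards, or moved to a worse level. Two separate frequency columns cannot answer it. A subject who was positive throughout and a subject who became positive on drug look the same in the post-dose column.

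Subjects may also enter with some ideation. Exclusion criterion 10 removes those at significant suicide risk, those scoring 5 or more on MADRS item 10, and those with an attempt in the 6 months before screening. A score of up to 4 without significant risk is allowed.

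**Working it through.** The plan states no figure on this point, so there is none to reproduce. The check has three parts.

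**1. What the two columns can identify**

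Let n be the group size, *pre* the number positive before dosing, *post* the number positive after dosing, and x the number of new-onset cases. The persisting cases number *post* − x. They cannot exceed *pre*, and x cannot exceed n − *pre*. So:

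max(0, *post* − *pre*) ≤ x ≤ min(*post*, n − *pre*)

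With n = 160 (Protocol 13.3) and assumed equal counts in both periods:

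| Positive in each period (assumed) | Possible new-onset cases |
|---|---|
| 16 (10%) | 0 to 16 |
| 48 (30%) | 0 to 48 |
| 80 (50%) | 0 to 80 |

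The tables are equally consistent with no new cases and with complete turnover. The visit table in 3.3.2.3 adds more separate columns but no link between them, so it does not narrow these limits to an actual count.

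**2. How far persisting ideation dilutes the comparison**

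Let b be the share with ideation before dosing, s the share of those still positive afterwards, and t the new-onset rate among the rest. The post-dose frequency is b·s + (1 − b)·t. With b and s the same in both groups, the difference between groups is (1 − b)(t_drug − t_placebo).

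The documents give neither b nor s, so ranges are assumed. For t, 6.6% and 1.6% are borrowed from CCT-003 for illustration. Those are adverse event rates in all subjects, not C-SSRS new-onset rates. Their ratio is 6.6 / 1.6 = 4.1 and their difference is 5.0 percentage points.

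Example: for b = 30% and s = 50%, drug is 0.15 + 0.7 × 0.066 = 19.6% and placebo is 0.15 + 0.7 × 0.016 = 16.1%.

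| b | Post-dose frequency at s = 50% | Ratio at s = 50% | Ratio for s = 25% to 75% | Difference |
|---|---|---|---|---|
| 10% | 10.9% vs 6.4% | 1.70 | 2.14 to 1.50 | 4.5 points |
| 30% | 19.6% vs 16.1% | 1.22 | 1.41 to 1.15 | 3.5 points |
| 50% | 28.3% vs 25.8% | 1.10 | 1.19 to 1.07 | 2.5 points |

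Over these ranges a new-onset ratio of 4.1 appears in the post-dose column as a ratio between 2.14 and 1.07. Randomisation should balance b, so this is dilution and not bias.

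**3. The same SAP, side by side**

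For laboratory values meeting the potentially clinically significant (PCS) criteria, SAP 3.3.1.1 crosses the entire pre-dose period with the entire post-dose period. SAP 3.3.2.4 uses the same two periods for the C-SSRS without crossing them. SAP Appendix 1 lists both tables as additions in Version 2.

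**The case against.** The strongest reply is that emergent suicidality is visible elsewhere.

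- The CCT-003 imbalance was itself an adverse event result. SAP 3.1.2 gives the like-for-like output: treatment-emergent events by preferred term, serious events, events leading to discontinuation and events over time.
- Protocol 10.1.3 requires ideation without a plan to be collected as an adverse event, and ideation with a plan or an attempt as a serious one.
- SAP 2.3 item (2) gives change from baseline in each MADRS item, including item 10, with differences from placebo and confidence intervals.

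All of this stands, and it refutes a stronger reading: that new suicidality on drug would go unseen in the trial's outputs altogether. Nor do the two protocol sentences on adverse events shut the C-SSRS out of that route. The one in 10.1.3 concerns conditions present at consent. The one in 10.2.1.2 is followed by an instruction to follow up anything the scale reveals and to report it normally if it proves to be an adverse event. What remains is that neither route counts subjects by change in C-SSRS category. Adverse event capture depends on the investigator's judgement, and a mean change in item 10 can improve while a few subjects worsen.

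A reader might also infer that the pre-dose column mixes lifetime history with current status. The documents do not show this. The screening-only items in SAP 3.3.2.3 are details of past attempts and are not variables in 3.3.2.4. What is missing is a statement of the look-back and of whether Screening counts within the entire pre-dose period.

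Three more points on the other side are fair. Dilution matters little for behaviour and the most severe ideation, given the exclusions and the separate rows for each level. The plan does deliver the descriptive statistics that the protocol promises. Shift tables are not universal in this SAP: vital signs and weight have none.

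**Conclusion.** The point holds for the C-SSRS tables. As planned, they cannot identify subjects with new or worsened ideation or behaviour after dosing, for any group size or result pattern in which some subjects are positive before dosing and some after. That conclusion needs no assumption beyond the table layout.

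The size of the dilution is illustrative only. It rests on assumed prevalence and persistence and on borrowed adverse event rates, so no fixed factor can be claimed for how much clearer a shift table would be. Nor does the point support a claim of biased comparison between groups.

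No confirmatory conclusion is affected. The change is still worth making, because the scale is a named safety endpoint, the programme has a reported prior imbalance, and the SAP already uses the needed layout for laboratory data.

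**What to change.** In SAP 3.3.2.4 add, by treatment group:

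1. A shift table of the worst pre-dose category by the worst category in the entire post-dose period, laid out as for the laboratory PCS results in 3.3.1.1. State the ordering of categories.
2. The number and percentage with new onset: none pre-dose, any post-dose. Denominator: subjects with none pre-dose.
3. The number and percentage with worsening: post-dose category above the worst pre-dose category. Denominator: subjects with both pre-dose and post-dose assessments who were not already in the highest category.

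Use one pre-dose reference for all three and write it into the SAP: all pre-dose visits including Screening, with any lifetime-history responses excluded. Leaving Screening out would label ideation recorded there as new.

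Keep the output descriptive, with no test. If 40% had ideation at baseline (assumed), 96 subjects per group would be at risk, and the borrowed rates would give about 96 × 0.066 = 6.3 and 96 × 0.016 = 1.5 cases, too few for a useful test.

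The cost is SAP wording and one more table to program. No new data are needed.

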21. The subject has clinically significant abnormal ECG as determined by the investigator, at the start of the screening period, placebo lead-in period, or double-blind treatment period.
22. The subject has clinically significant abnormal findings of clinical laboratory tests as determined by the investigator, or has alanine aminotransferase (ALT) or aspartate aminotransferase (AST) $>2 \times$ ULN at the start of screening period or placebo lead-in period.
23. If female, the subject is pregnant or lactating.
24. The subject has a disease or takes medications that could, in the opinion of the investigator, interfere with the evaluation of the safety, tolerability, or efficacy.
25. The subject is, in the opinion of the investigator, unsuitable for this study for any other reason.

<Justification for Exclusion Criteria>

Criteria 1, 4, and 5 were set to exclude subjects or the possible subjects with concurrent mental or neurological disorder other than MDD and to adequately evaluate the efficacy and safety for the target disease.

Criterion 2 was set to exclude subjects or the possible subjects with refractory major depression and include adequate subjects for the evaluation of drug effect.

Criterion 3 was set to exclude subjects who have received augmentation therapy and include adequate subjects for the evaluation of drug effect since subjects who are required to receive augmentation therapy may have refractory major depression or concurrent mental or neurological disorder other than MDD.

Criterion 6 was set to exclude subjects who highly respond to placebo and include adequate subjects for the evaluation of drug effect. Subjects who abruptly worsen their symptoms in a short time are also excluded from the study in consideration of the appropriateness of drug effect evaluation and the safety of subjects.

Criterion 7 was set because it influences the evaluation in the placebo lead-in period.

Criteria 8, 9, 11 to 13 were set because they could influence the evaluation of efficacy.

Criteria 10, 17 to 22 were set with respect to the safety of subjects.

Criteria 14 and 24 were set because they could influence the evaluation of efficacy and safety.

Criterion 15 was set because the bias toward Lu AA21004 based on their treatment experience could influence the evaluation of the efficacy and safety.

Criterion 16 was set to avoid duplicated evaluation of subjects.

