1.2 Demographics and Other Baseline Characteristics	13
1.2.1 Summary of Demographics and Other Baseline Characteristics	13
1.2.2 Medical History and Concurrent Medical Conditions	15
1.2.3 Medication History and Concomitant Medications	16
1.3 Treatment Compliance.....	16
1.3.1 Study Drug Exposure and Compliance.....	16
2 Efficacy Analysis.....	17
2.1 Primary Endpoint(s) and Analytical Methods.....	17
2.1.1 Primary Analysis.....	17
2.1.2 Secondary Analysis (1).....	18
2.1.3 Secondary Analysis (2).....	18
2.2 Secondary Endpoint(s) and Analytical Methods.....	19
2.3 Other Analysis/Additional Endpoint(s) and Analytical Methods	22
2.4 Statistical/Analytical Issues	31
2.4.1 Adjustments for Covariates.....	31
2.4.2 Handling of Dropouts or Missing Data.....	31
2.4.3 Interim Analyses and Data Monitoring.....	31
2.4.4 Multicenter Studies	31
2.4.5 Multiple Comparison/Multiplicity	31
2.4.6 Use of an “Efficacy Subset” of Subjects.....	32
2.4.7 Active-Control Studies Intended to Show Equivalence or Non-Inferiority	32
2.4.8 Examination of Subgroups.....	32
3 Safety Analysis	33
3.1 Treatment-Emergent Adverse Event.....	33
3.1.1 Overview of Treatment-Emergent Adverse Events	33

3.1.2 Displays of Treatment-Emergent Adverse Events.....	34
3.2 Pretreatment Events and Placebo Lead-in Adverse Events	35
3.2.1 Displays of Pretreatment Events.....	35
3.2.2 Displays of Placebo Lead-in Adverse Events	36
3.3 Laboratory and Other Safety Data	37
3.3.1 Laboratory Test Results	37
3.3.2 Vital Signs, Physical Findings and Other Observations Related to Safety.....	38
4 Significance Level and Confidence Coefficient	44
Amendment History (Version Management).....	45
[Appendix 1] Change Comparison Table for Lu AA21004/CCT-004	1
[Appendix 2]Definition of PCS Criteria	1

Glossary

- Treatment-emergent adverse event (TEAE): An adverse event which occurs on or after the start of double-blind study drug
- Placebo lead-in adverse event: An adverse event which occurs on or after the start of placebo lead-in study drug before the start of double-blind study drug
- Drug-related adverse event: An adverse event that is considered to be either probable, or possible related to the double-blind study drug will be treated as related.
- Descriptive statistics: number of subjects, mean, standard deviation, maximum, minimum, and quartiles
- PCS: Potentially Clinically Significant

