- Study Day: The day before the first dose of the double-blind study drug will be defined as Study Day -1 and the day of the first dose will be defined as Study Day 1.
- Follow-up Day: The day after the last dose of the double-blind study drug will be defined as Follow-up Day 1.
- Treatment Groups: Placebo, Lu AA21004 10 mg, Lu AA21004 20 mg
- MADRS total score: Sum of the 10 MADRS items
- HAM-D17 total score: Sum of the 17 HAM-D items
- HAM-D21 total score: Sum of the 21 HAM-D items
- SDS total score: Sum of the 3 SDS items
- MADRS response: Percentage of subjects whose MADRS total score decreased by a greater than or equal to 50% from baseline
- MADRS remission: Percentage of subjects whose MADRS total score decreased to 10 or less

Definition of TIME WINDOW

For each test/observation/evaluation item, all evaluable data (non-missing and acceptable according to the “Handling Rules for Analysis Data”) will be handled according to the following rules.

For each visit other than Week 8 (LOCF), observation in the corresponding time interval will be used. If more than one observation lies within the same visit window, the observation with the closest Study Day to the scheduled Study Day will be used. If there are two observations equidistant to the scheduled Study Day, the later observation will be used. The difference from the scheduled Study Day will be judged based on the Study Day and Follow-up Day.

For Week 8 (LOCF), the last observation obtained in the corresponding time interval will be used.

MADRS, CGI-S

Visit	Scheduled Study Day (days)	Time Interval (days)	
		Study Day	Follow-up Day
Screening	Study Day: -22	<= -12	-
Placebo lead-in	Study Day: -8	-11 - -5	-
Baseline (Week 0)	Study Day: -1	-4 - 1	-
Week 1	Study Day: 7	2 - 10	<8
Week 2	Study Day: 14	11 - 21	<8
Week 4	Study Day: 28	22 - 35	<8
Week 6	Study Day: 42	36 - 49	<8
Week 8	Study Day: 56	50 <=	<8
Week 8 (LOCF)	-	2 <=	<8

HAM-D

Visit	Scheduled Study Day (days)	Time Interval (days)	
		Study Day	Follow-up Day
Screening	Study Day: -22	<= -12	-
Placebo lead-in	Study Day: -8	-11 - -5	-
Baseline (Week 0)	Study Day: -1	-4 - 1	-
Week 8	Study Day: 56	2 <=	<8
Week 8 (LOCF)	-	2 <=	<8

CGI-I

Visit	Scheduled Study Day (days)	Time Interval (days)	
		Study Day	Follow-up Day
Baseline (Week 0)	Study Day: -1	<= 1	-
Week 1	Study Day: 7	2 - 10	<8
Week 2	Study Day: 14	11 - 21	<8
Week 4	Study Day: 28	22 - 35	<8
Week 6	Study Day: 42	36 - 49	<8
Week 8	Study Day: 56	50 <=	<8
Week 8 (LOCF)	-	2 <=	<8

SDS

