3.3.2 Vital Signs, Physical Findings and Other Observations Related to Safety

3.3.2.1 Vital Signs and Weight

Analysis Set: Safety Analysis Set

Analysis Temperature

Variable(s): Systolic Blood Pressure

Diastolic Blood Pressure

Pulse Rate

Weight

Categories: Results based on PCS [Meet PCS Criteria, Does not meet PCS Criteria]
Criteria

Visit: Temperature, Systolic Blood Pressure, Diastolic Blood Pressure, Pulse Rate:
Screening, Placebo Lead-in, Baseline, Week 1, Week 2, Week 4, Week 6, and
Week 8

Weight: Screening, Placebo Lead-in, Baseline, Week 4, and Week 8

PCS: Entire post-dose period

Analytical The following summaries will be provided for the above analysis variable(s).

Method(s):
(1) Descriptive statistics for observed values at each visit and changes from
baseline at each visit (each post-dose visit [Week 1 to Week 8] - Baseline)
(2) Plots over time for each subject
(3) Frequency distributions of the results based on PCS Criteria during the

entire post-dose period
 Refer to the Appendix of this Statistical Analysis Plan if a vital sign parameter has lower or upper PCS Criteria.

3.3.2.2 12-lead ECG

Analysis Set: Safety Analysis Set
 Analysis RR Interval
 Variable(s): PR Interval
 QT Interval
 QRS Interval
 QTcB Interval
 QTcF Interval
 12-Lead ECG Interpretation [Within Normal Limits, Abnormal but not Clinically Significant, Abnormal and Clinically Significant]
 Categories: Results based on PCS [Meet PCS Criteria, Does not meet PCS Criteria]
 Visit: Screening, Placebo Lead-in, Baseline, Week 4, and Week 8
 PCS: Entire post-dose period
 Analytical For each variable other than 12-lead ECG interpretations, summaries (1) to (3) will be provided by treatment group.
 Method(s): For 12-lead ECG interpretation, summary (4) will be provided by treatment group.
 (1) Descriptive statistics for observed values at each visit and changes from baseline at each visit (each post-dose visit [Week 4, Week 8] - Baseline)
 (2) Plots over time for each subject
 (3) Frequency distributions of the results based on PCS Criteria during the entire post-dose period
 Refer to the Appendix of this Statistical Analysis Plan if a ECG laboratory parameter has lower or upper PCS Criteria.
 (4) Shift tables at baseline and each post-dose visit

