	SI	mmol/L	Measured value is \leq 125 or \geq 155
Calcium	CV	mg/dL	Measured value is \leq 0.8-fold of LLN or \geq 1.2-fold of ULN
	SI	mmol/L	Measured value is \leq 0.8-fold of LLN or \geq 1.2-fold of ULN
Triglycerides	CV	mg/dL	Measured value is \geq 1.5-fold of ULN
	SI	mmol/L	Measured value is \geq 1.5-fold of ULN
Total Cholesterol	CV	mg/dL	Measured value is \geq 1.5-fold of ULN
	SI	mmol/L	Measured value is \geq 1.5-fold of ULN
HDL Cholesterol	CV	mg/dL	Measured value is \geq 1.5-fold of ULN
	SI	mmol/L	Measured value is \geq 1.5-fold of ULN
LDL Cholesterol	CV	mg/dL	Measured value is \geq 1.5-fold of ULN
	SI	mmol/L	Measured value is \geq 1.5-fold of ULN

Vital Signs (Blood Pressure, Pulse Rate) and Weight

Analysis Variable(s):	Unit	Definition of PCS
Pulse Rate	bpm	Measured value is ≤ 50 and change* is ≤ -15 or measured value is ≥ 120 and change* is ≥ 15
Diastolic Blood Pressure	mmHg	Measured value is ≤ 50 and change* is ≤ -15 or measured value is ≥ 105 and change* is ≥ 15
Systolic Blood Pressure	mmHg	Measured value is ≤ 90 and change* is ≤ -20 or measured value is ≥ 180 and change* is ≥ 20
Weight	kg	Change rate* is $\leq -7\%$ or $\geq 7\%$

*: Change or change rate from baseline

Resting 12-lead ECG

Analysis Variable(s):	Unit	Definition of PCS
PR Interval	msec	Measured value is < 120 or ≥ 250
QRS Interval	msec	Measured value is < 40 or > 150
QT Interval	msec	Measured value is < 280 or > 500
QTcF Interval	msec	Measured value is < 340 and change* is < -60 or measured value is > 500 and change* is > 60
QTcB Interval	msec	Measured value is < 340 and change* is < -60 or measured value is > 500 and change* is > 60
RR Interval	msec	Measured value is < 500 and change* is ≤ -200 or measured value is > 1200 and change* is ≥ 200

*: Change from baseline

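### The QTcF and QTcB significance rule needs both limits at once, so no table counts by arm QTc above 500 ms alone or a rise above 60 ms alone; two added counts would close the gap (minor).

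*SAP*

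**What the plan says.** SAP Appendix 2, Resting 12-lead ECG, gives QTcF and QTcB the same rule: "Measured value is < 340 and change* is < -60 or measured value is > 500 and change* is > 60", with change taken from baseline. RR has the same form (it begins "Measured value is < 500 and change* is"), as do pulse and systolic and diastolic pressure. PR, QRS and uncorrected QT are judged on the value alone, and weight on relative change alone. The joint form therefore covers 6 of the 10 vital-sign and ECG rows.

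SAP 3.3.2.2 states: "For each variable other than 12-lead ECG interpretations, summaries (1) to (3) will be provided by treatment group". For QTc these are (1) descriptive statistics by visit, (2) a plot for each subject, and (3) "Frequency distributions of the results based on PCS Criteria during the entire post-dose period", with two categories, meets or does not meet. Output (4) is a shift table of the investigator's ECG interpretation.

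Protocol 13.1.5 promises incidences of potentially clinically significant values but sets no QTc limit.

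**The concern.** A subject can pass one QTc limit and miss the other. Such subjects join everyone else in the does-not-meet row, and output (3) is the only planned output that sets QTc against a number. A reader comparing arms could not tell from the tables how many subjects passed 500 ms, or how many rose by more than 60 ms. In the same appendix an uncorrected QT of 501 ms is counted on its value alone, while a QTc of 520 ms reached from 470 ms is not. What is at stake is the completeness of a descriptive safety comparison.

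**Working it through.** **The rule as logic.** With baseline b and post-dose value v, a subject is counted if (v < 340 and v − b < −60) or (v > 500 and v − b > 60). No other grouping of the and/or terms can be satisfied.

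**Worked cases (ms).**
- 470 to 520 (+50): not counted
- 441 to 501 (+60): not counted
- 440 to 501 (+61): counted
- 439 to 500 (+61): not counted
- 400 to 495 (+95): not counted
- 420 to 505 (+85): counted

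In whole milliseconds, a value above 500 with a rise of 60 or less needs a baseline of 441 or higher. A rise above 60 ending at 500 or below needs a baseline of 439 or lower. On the high side the rise must exceed max(60, 500 − b): 100 from 400, 80 from 420, and 60 from 440 upward.

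**Can both baselines enter?** Yes. Protocol 7.2, criterion 21, excludes on judgement ("The subject has clinically significant abnormal ECG as determined by the investigator") and gives no numeric QTc limit.

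**What else shows these subjects?**
- Output (1) follows the SAP Glossary ("Descriptive statistics: number of subjects, mean, standard deviation, maximum, minimum, and quartiles"), so the arm maximum and minimum appear at each visit. They show whether a limit was passed, not by how many subjects. Each visit uses one ECG per window ("the observation with the closest Study Day to the scheduled Study Day will be used"); with one scheduled ECG at Week 4 and one at Week 8, that matters only for unscheduled or early-termination ECGs.
- The plots show individual values but are not a tabulated count.
- Uncorrected QT above 500 ms, the interpretation shift table and the adverse event tables are by arm, but none is tied to a QTc limit.

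**Illustrative size.** The documents give no QTc distribution. Assumed: normal values, baseline mean 400 to 420, baseline SD s_b = 20 to 25, SD of change s_c = 15, 20 or 25, one visit. The 160 per arm is from Protocol 13.3. Two models are used:
- Equal SDs at baseline and post-dose: correlation r = 1 − s_c²/(2 s_b²).
- Change independent of baseline: post-dose SD = √(s_b² + s_c²).

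Rises above 60: 160 × P(Z > (60 − mean rise)/s_c), the same in both models. Joint count: 160 × P(v > max(500, b + 60)), integrated over the distribution of b.

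| Mean rise | s_c | Rises > 60 | Joint, equal SDs | Joint, independent change |
|---|---|---|---|---|
| 20 | 15 | 0.61 | 0.0006–0.035 | 0.03–0.17 |
| 20 | 20 | 3.64 | 0.003–0.21 | 0.23–1.1 |
| 20 | 25 | 8.77 | 0.005–0.52 | 0.82–3.1 |
| 0 | 15, 20, 25 | 0.005, 0.22, 1.31 | at most 0.025 | at most 0.43 |

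Under the 20 ms rise, the joint rule counts at most 0.52/8.77 = 6% (equal SDs) or 3.1/8.77, about 36% (independent change), of subjects rising above 60. Outside the assumed range, at baseline mean 430 with independent change and both SDs 25, it counts 4.4 of 8.8, about half.

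Values above 500 with no drug effect, at mean 420 and SDs of 25:
- Equal SDs: 160 × P(Z > 80/25) = 0.11.
- Independent change: √(25² + 25²) = 35.4, and 160 × P(Z > 80/35.4) = 1.9.

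**The case against.** The strongest reply is that nothing is wrong. The joint form is applied consistently, Protocol 13.1.5 sets no QTc limit, and a table built on Appendix 2 keeps its promise. That stands: a reader might infer that the rule is a drafting error or breaks the protocol, and the documents support neither.

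A second reply is that existing outputs go far. If an arm's maximum value is 500 ms or less and its maximum change is 60 ms or less, the count for the summarised ECGs at that visit is exactly zero. That also stands. It defeats any claim that such cases would be invisible, but it gives no number once a limit is passed.

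A third is that the only QT evidence cited points to no effect: Protocol 4.1.2 reports no potential for prolongation up to 40 mg/day, twice the top dose here. The 20 ms rise is therefore a stress case, and with no effect the added rows would mostly show chance flags. That is fair and is why the point is minor.

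A reader might also infer that the joint count would stay near zero even under a real shift. This holds only under the equal-SD model. With change independent of baseline it reaches 3.1 per arm, and the documents do not favour either model.

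**Conclusion.** The point holds as a cheap improvement to descriptive safety tables, not as an error in the plan. The absence of separate by-arm QTc counts follows from the wording of Appendix 2 and the output list in 3.3.2.2 and needs no assumption. The size is illustrative only. Within the assumed ranges, both models leave most subjects with a rise above 60 ms uncounted under a 20 ms mean rise, but how close the joint count comes to zero depends on the model and on the baseline mean. Given the cited QT evidence, the expected effect is small. No efficacy result, including the primary analysis, is affected.

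**What to change.** Leave Appendix 2 and the joint count as they are. Add to SAP 3.3.2.2, by treatment group over the entire post-dose period, for QTcF and for QTcB, the number and percentage of subjects with:
- (i) any post-dose value above 500 ms, showing how many were already above 500 ms at baseline;
- (ii) any increase from baseline above 60 ms.

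These are the SAP's own limits. Showing baseline status follows SAP 3.3.1.1 (5), which already plans "Shift tables of the results based on PCS Criteria at baseline (entire pre-dose period) and during the entire post-dose period" for laboratory values.

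Produce the QTcF rows only after the QTcF formula in the SAP's Others list, after the time windows, has been confirmed; that is a separate matter. QTcB is recorded on the eCRF and does not wait for it.

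The cost is six short rows (three for each correction) from data already collected, plus some chance flags. With no drug effect, under the assumptions above, expect 0.005 to 1.3 rises above 60 ms per arm per visit for each correction, so at most 2 × 1.31 = 2.6 over Weeks 4 and 8; unscheduled ECGs would add to this. Values above 500 ms would be expected in 0.11 or fewer subjects per arm per visit with equal SDs, or up to 1.9 with change independent of baseline.
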